Platelet Transfusion During Neonatal Open Heart Surgery

NCT03045068

Version Date: 03/04/2020

Title: Neurodevelopmental Outcome and Platelet Transfusion During Neonatal Open Heart Surgery

Principal Investigator:

General Pediatrics (The High Risk Clinic)-

[name] - Study Design, Patient recruitment, Data Collection, and Data Analysis

Co Investigators:

Anesthesiology-

[name] (Anesthesiology) – Study Design, Patient recruitment, Data Collection and Data Analysis

[name], Clinical RA - Study Design, Patient recruitment, Data Collection and Data Analysis General Pediatrics (The High Risk Clinic)-

[name] – Study Design, Patient recruitment, Data Collection and Data Analysis Pediatric Cardiology-

[name] – Study Design, Patient recruitment, Data Collection, and Data Analysis Pediatric Cardiac Surgery-

[name] – Study Design, Data Collection, and Data Analysis

[name], CPN – Patient Recruitment, Data Collection, and Data Analysis

Hypothesis:

Dilutional thrombocytopenia after cardiopulmonary bypass (CPB) is universal and there is a recent data supporting administration of donor apheresis platelets just prior to termination of bypass assist in early correction of coagulopathy, early hemostasis and lesser donor exposure of blood products after cardiac surgery. This administration of donor apheresis platelets just prior to termination of bypass also assist in favorable neurodevelopmental outcome.

Background:

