Congenital heart disease (CHD) affects about 40,000 births per year in the United States, making it the most common type of birth defect.¹ Advancements in management, either operative or non-operative, for infants with CHD have improved early mortality in this patient population over the past 2-3 decades.² However, with improved survival the focus has turned to the neurodevelopmental outcomes of these patients. Studies have begun to elucidate evidence of neurodevelopmental delay in children with CHD, manifest as behavioral difficulties, executive function impairment, attention deficit hyperactivity disorder (ADHD), and other related symptoms.^{3, 6} In a prospective cohort study by Medoff-Cooper *et al.*, poor feeding skills and delayed growth rate were suggested as identifying factors for neurodevelopmental disability risk in infants with complex CHD who underwent cardiac intervention within 30 days of birth.⁴ As more infants with complex CHD survive early cardiac intervention, there has also been a growing interest to provide these patients with appropriate resources and/or interventions.⁵

It is known that CPB has been associated with risk for cerebral hypoxic-ischemic/reperfusion injury and embolic complications. However, there are few data to demonstrate details of the CPB and neurodevelopment in the patients with CHD. In a previous study in this institution (IRB#: HSC-MS-16-1034), an administration of donor apheresis platelets just prior to termination of bypass has demonstrated distinct advantages of earlier achievement of hemostasis, reduction in post-CPB transfusion, and improved postoperative outcome (significantly less mediastinal exploration for bleeding, duration of mechanical ventilation, and length of intensive care unit stay). The principal aim of this study is to understand whether the benefit of the timing of the platelet administration extends to the neurodevelopment outcome in the same patient population studied in the previous study.

Objectives:

Primary objectives – To evaluate any significant neurodevelopment differences between two groups: administration of donor apheresis platelets just prior to termination of bypass versus standard transfusion of platelet apheresis after modified ultrafiltration and protamine administration. A standardized assessment tools, Bayley Scales of Infant and Toddler Development 3rd edition (looking into five major

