areas of development: cognitive, language (expressive/receptive), motor (gross/fine), will be used to evaluate the study populations' development at around 2 year of age.

Secondary objectives – To seek to provide improved intervention with long term improvement in quality of life for the patients.

Study Method:

Prospective cohort study comparing neurodevelopment between patients who underwent platelet apheresis transfusion prior to termination of CPB versus standard transfusion of platelet apheresis after modified ultrafiltration and protamine administration.

Study Population:

We will be including all the patients reviewed in the previous study in this institution (IRB#: HSC-MS-16-1034)

Treatment group -

Platelet Transfusion Management

- Pre-Termination of CPB- Platelet Transfusion 10ml/kg to be administered to the patient via central venous access when the patient has been rewarmed to 35*C, (the Sano or BT shunt clip is still on in children with SV physiology)
- 2. Post CPB- Platelet transfusion 10ml/kg via a central venous line is continued at a rate of 100 ml/hour till completion.

FFP and Cryoprecipitate:

- 1. 1 unit of cryoprecipitate administered during MUF and or after MUF as needed
- 2. FFP transfusion 10ml/kg during MUF and or after MUF as needed

PRBC and cell saver Transfusion:

1. Transfuse for target Hematocrit > 40 in neonates with SV physiology; Transfuse for Hematocrit> 33 for 2-Ventricle physiology

3- Factor Concentrate (Bebulin):

1. Based on clinical bleeding and achievement of hemostasis

Control Group –

Platelet Transfusion Management

- 1. Pre-Termination of CPB- No intervention
- 2. Post CPB- Platelet transfusion 20ml/kg via a central venous line is continued at a rate of 100 ml/hour till completion.
 - a. Initial transfusion to occur proximal to the hemofilter on the MUF circuit for as long as MUF lasts
 - b. Subsequent platelet transfusion continued till completion via central venous access to the patient

FFP and Cryoprecipitate:

- 1. 1 unit of cryoprecipitate administered during MUF and or after MUF as needed
- 2. FFP transfusion 10ml/kg during MUF and or after MUF as needed

PRBC and cell saver Transfusion:

- 1. Transfuse for target Hematocrit > 40 in neonates with SV physiology; Transfuse for Hematocrit> 33 for 2-Ventricle physiology
- 3 Factor Concentrate (Bebulin):

1. Based on clinical bleeding and achievement of hemostasis

Study Procedures:

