Either a written informed consent or verbal informed consent over the phone will be obtained. The patients will be referred to the High Risk Clinic, where a neuropsychiatrist will be performing the Bayley Scales of Infant and Toddler Development at around 2 year old. The High Risk Clinic currently acts as a medical home for patients with chronic illness requiring multiple different specialty needs. We will be utilizing the developmental assessment aspect of the clinic.

Data and Safety Monitoring:

We do not anticipate any direct adverse events.

All data collected will be entered into a secure electronic database that will be encrypted and password protected (https://med.uth.edu/msit/secure-share/). The UT Secure-share sheet will be shared only with the co-investigators. A log-linking file will be maintained to keep patient information separate from the data collection sheet. No paper copies will be maintained.

Statistics**:

We will present data using following statistics, as appropriate and as applicable:

Mean with standard deviation/Median with interquartile range where applicable for continuous variables. Differences in continuous variables will utilize Wilcoxon sum rank test (e.g. *P*-values for age, weight and head circumference, and results of standardized assessment tool as appropriate)

Differences in categorical variables will utilize either Chi-square test or Fisher's exact test (e.g. *P*-values for gender, types of CHD, other diagnoses (e.g. genetics), types of operation/procedures, and results of standardized assessment tool as appropriate)

P-values <0.05 will be considered as statistically significant

**Statistics methods are subject to change to most appropriately present data

Ethics

IRB review will be requested by UTHealth's IRB

See above Data and Safety monitoring in regard to our plan to protect privacy of subjects Appropriate consent and documentation of informed consent will be sought

References:

- Centers of Disease Control and Prevention. Congenital Heart Defects (CHDs): Data & Statistics. Centers of Disease Control and Prevention [CDC website]. November 7, 2016. Available at: https://www.cdc.gov/ncbddd/heartdefects/data.html. Accessed March 30, 2019.

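### Five Bayley areas serve one primary question, each tested at 0.05, with no primary area and no multiplicity rule

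*Combined protocol and SAP*

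**What the plan says.** The Background sets a single principal aim: to learn "whether the benefit of the timing of the platelet administration extends to the neurodevelopment outcome". The Hypothesis is directional: giving platelets just before the end of bypass should "also assist in favorable neurodevelopmental outcome".

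The primary objective (Objectives) is "To evaluate any significant neurodevelopment differences between two groups", measured with the Bayley Scales, third edition, at around two years of age. The text counts five "areas of development: cognitive, language (expressive/receptive), motor (gross/fine").

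The Statistics section assigns the Wilcoxon rank-sum test to continuous variables and chi-square or Fisher's exact test to categorical ones. It lists "results of standardized assessment tool as appropriate" under both. It then states "P-values <0.05 will be considered as statistically significant", with no separate rule for the primary objective. A footnote allows the methods to be changed. No section names a primary area, a testing order, a multiplicity adjustment or a criterion for calling the primary objective met.

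**The concern.** One question is to be answered by five results, each judged against 0.05 on its own. The wording of the objective fits a reading in which any single significant area counts as a positive answer, and no other sentence excludes that reading. A chance result in one area could then be presented as support for the directional hypothesis, at an error rate well above the one the threshold suggests.

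Two features widen the opening. The plan does not settle whether Bayley results are compared as scores or as categories, and the footnote leaves the methods open. Every listed investigator role also combines data collection with data analysis (the principal investigator's entry reads "Study Design, Patient recruitment, Data Collection, and Data Analysis"), and the plan sets no point at which the primary analysis is fixed. A primary area, or a choice between scores and categories, would not be credible if made after results had been seen by group.

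**Working it through.** The plan gives no sample size, power or overall error rate, so there is no stated figure to reproduce.

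**Inputs**
- From the plan: five areas (Objectives); threshold 0.05 for each P-value (Statistics).
- Assumed: two-sided tests, since sidedness is not stated and the objective asks about any difference. This leaves 0.025 per test in the favourable direction.
- Assumed: one test per area, no true difference in any area, and a common correlation ρ between the five test statistics, shown from 0 to 0.9.

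**Uncorrelated areas**
- Either direction: 1 − 0.95^5 = 1 − 0.7738 = 22.6%.
- Favourable direction: 1 − 0.975^5 = 1 − 0.8811 = 11.9%.
- Holm over five: when no area differs, a false claim requires the smallest P-value to pass 0.05/5 = 0.01. This gives 1 − 0.99^5 = 1 − 0.9510 = 4.9%.

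**Correlated areas**

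Write each statistic as √ρ·U + √(1−ρ)·E_j, with U and E_j independent standard normal. With φ and Φ the standard normal density and distribution function, the chance that at least one exceeds c in absolute value is

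1 − ∫ [Φ((c − √ρ·u)/√(1−ρ)) − Φ((−c − √ρ·u)/√(1−ρ))]^5 φ(u) du.

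Here c = 1.960 for the plan as written and c = 2.576 for the first Holm step. For the favourable direction the second Φ term is dropped.

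| ρ | Any P<0.05 | Any favourable P<0.05 | Holm, either direction | Holm, favourable |
|---|---|---|---|---|
| 0 | 22.6% | 11.9% | 4.9% | 2.5% |
| 0.4 | 19.7% | 9.9% | 4.5% | 2.2% |
| 0.6 | 16.7% | 8.3% | 3.9% | 1.9% |
| 0.8 | 12.7% | 6.4% | 3.0% | 1.5% |
| 0.9 | 10.2% | 5.1% | 2.3% | 1.2% |

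Relative to 2.5%, the favourable-direction rate is 0.1189/0.025 = 4.8 times at ρ = 0 and 0.0508/0.025 = 2.0 times at ρ = 0.9.

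**Check with the planned test.** Wilcoxon tests were simulated on five correlated scores, 20,000 replicates each, with assumed group sizes:
- 20 per group: 22.8% / 12.4% (either / favourable direction) at ρ = 0, and 10.7% / 5.4% at ρ = 0.9.
- 50 per group: 22.4% / 11.5% at ρ = 0, and 10.5% / 5.0% at ρ = 0.9.

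**One primary area, the other four under Holm**
- With a gate (the four are tested only if the primary area is significant) and no area differing: 5.0% at every ρ, because any false claim must first pass the primary test.
- If the primary area truly differs and always passes, the first Holm step for the other four is 0.05/4 = 0.0125. The chance of a false claim among them is 1 − 0.9875^4 = 4.9% at ρ = 0, then 4.5%, 4.0%, 3.2% and 2.6% as ρ rises to 0.9.
- Without the gate and with no area differing: 9.7%, 8.8%, 7.7%, 6.4% and 5.5%. The gate is therefore needed.

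**Power cost of 0.01 instead of 0.05**
- Detectable difference at 80% power: (2.576 + 0.842)/(1.960 + 0.842) = 1.22, so 22% larger.
- A difference with 80% power at 0.05 has power Φ(2.802 − 2.576) = 58.9% at 0.01.
- If all five areas differ by that amount, the chance that at least one passes 0.01 is 98.8%, 91.8%, 86.2%, 78.5% and 72.9% as ρ goes from 0 to 0.9.

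**The case against.** The strongest reply is that the plan contains no rule making one significant area a positive trial. The objective can be read as a broad descriptive aim, and the 0.05 threshold also covers baseline comparisons such as age and sex. Under a stricter reading, such as at least two significant areas of five, the two-sided rate would be about 2% at ρ = 0 and 6% at ρ = 0.9. This stands as a limit: the figures describe one permitted way of reporting, not a fixed property of the plan. It does not remove the gap, because the plan states no stricter rule either.

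Other objections narrow the size or scope:
- **Correlation.** Zero correlation among five areas of one instrument in the same child is a bound, not an expectation. At 0.4 to 0.8 the range is 19.7% to 12.7% two-sided. Nor is 0.9 a floor: 0.95 gives 8.5% two-sided and 4.2% favourable, still above nominal.
- **Number of tests.** The list could be read as three headings, two of them subdivided. Three tests would give 14.3% at ρ = 0 and 8.4% at ρ = 0.9. The Objectives do say five.
- **Who assesses.** The Bayley is performed by a neuropsychiatrist in the High Risk Clinic, and shared roles do not show that results are seen by group before analysis choices are made. That is fair, but the plan still sets no point at which those choices are fixed.
- **Comparability.** This is described as a cohort study, and no randomisation is stated. If the groups are not comparable, no multiplicity rule guarantees 5%. That is a separate matter.
- **Calling it exploratory.** Labelling every area exploratory would avoid a false claim at no power cost. It would also give up the stated hypothesis and primary objective, and the plan nowhere describes itself as exploratory.

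**Conclusion.** The concern holds. The absence of a primary area, testing order and multiplicity rule is plain in the text. If one significant area of five is reported as a positive primary finding, the false-positive chance is about 10% to 23% instead of 5%, and about 5% to 12% instead of 2.5% in the favourable direction. That is two to nearly five times the directional error of a single test.

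These ranges rest on two-sided testing, one test per area, comparable groups and an assumed correlation of 0.9 down to 0. The freedom to choose scores or categories, or to change methods, would add to them by an amount that cannot be computed from the documents. This should be fixed: it bears on how the primary result can be interpreted.

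**What to change.** In Objectives and Statistics, adopt one of the following.

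- **(a) One primary area.** The investigators name one Bayley area as primary, analysed as a continuous score by Wilcoxon at two-sided 0.05. The other four are tested under Holm at 0.05 only if the primary is significant; otherwise they are reported as descriptive.
- **(b) Five primary areas.** All five remain primary, analysed as continuous scores by Wilcoxon under Holm at an overall two-sided 0.05.

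In either case, report all five areas and label category results as descriptive. Replace the footnote with: *The primary analysis is fixed in a dated, signed document before any Bayley results are reviewed by group; any later change is reported as post hoc.* If results have already been reviewed by group, use (b), which requires no choice of area, and state that it was adopted post hoc.

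The change needs no new data or visits, but it costs power. Under (a), a difference confined to another area cannot carry the primary claim. Under (b), the loss shown in the working cannot be offset by recruiting more patients, because the population is set by the earlier study: "We will be including all the patients reviewed in the previous study in this institution".
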